**Blinding**

The investigator will not be provided with randomization codes. The codes will be maintained within the IWRS, which has the functionality to allow the investigator to break the blind for an individual subject.

Data that may potentially unblind the study drug assignment (ie, study drug serum concentrations, anti-JNJ-64565111 antibodies, study drug preparation/accountability data, study drug allocation, FPG, HbA1c, serum  $\beta$ -hydroxybutyrate, and urine ketones) will be handled with special care to ensure that the integrity of the blind is maintained and the potential for bias is minimized. This can include making special provisions, such as segregating the data in question from view by the investigators, clinical team, or others as appropriate until the time of database lock and unblinding.

Under normal circumstances, the blind should not be broken until all subjects have completed the study and the database is locked. The investigator may in an emergency determine the

identity of the study drug by contacting the IWRS. While the responsibility to break the study drug code in emergency situations resides solely with the investigator, it is recommended that the investigator contact the sponsor or its designee if possible to discuss the particular situation, before breaking the blind. In the event the blind is broken, the sponsor must be informed as soon as possible. The date and reason for the unblinding must be documented in the appropriate section of the eCRF and in the source document. The documentation received from the IWRS indicating the code break must be retained with the subject's source documents in a secure manner so as not to unblind the treatment assignment to the study site or sponsor personnel. The investigator is also advised not to reveal the study treatment assignment to the study site (except as necessary for the clinical management of the subject) or sponsor personnel.

In general, treatment codes will be disclosed fully only after the study is completed and the clinical database is closed.

## 2. GENERAL ANALYSIS DEFINITIONS

### 2.1. Visit Windows

As subjects do not always adhere to the protocol visit schedule, the following rules are applied to assign actual visits to analysis visits. Listed below are the visit windows and the target days for each visit. The reference day is Study Day 1 (date of first dose). If a subject has 2 or more actual visits in one visit window, the visit closest to the target day will be used as the protocol visit for that visit window. The other additional visit(s) will not be used in the summaries or analyses but they can be used for determination of clinically important endpoints. If 2 actual visits are equidistant from the target day within a visit window, the later visit is used.

All assignments will be made in chronological order. Once a visit date is assigned to a visit window, it will no longer be used for a later time point except for the endpoint. Listed below (Table 2.1.1) are the visit windows and the target days for each visit defined in the protocol. A Post-Week 12 window was created to account for subjects who returned at a timepoint after the Week 12 visit window.

**Table 2.1.1: Visit Windows**

Parameter	Scheduled Visit Number	Time Interval (label on output)	Time Interval (Day) a	Target Time Point (Day)
All	2	Baseline	≤1 b	1
	3	Week 2	1 c -28	15
	4	Week 6	29-64	43
	5	Week 12	65-105	85
	6	Post-Week 12	≥106	

a Relative to the day of the first dose of double-blind study medication.

b Up to the first dose of double-blind study medication.

## **2.2. Analysis Sets**

### **2.2.1. All Randomized Analysis Set**

The all randomized analysis set will include all subjects who are randomly assigned to a treatment group.

### **2.2.2. Efficacy Analysis Sets**

- The intent-to-treat (ITT) analysis set will include all subjects who are randomly assigned to a treatment group and have a baseline body weight measurement.
- The modified intent-to-treat (mITT) analysis set includes all ITT subjects who have taken at least one dose of study medication and have at least 1 post-baseline body weight measurement.
- The completers' analysis set will consist of all mITT subjects who have completed 12 weeks of treatment (i.e., documented in the Treatment Disposition eCRF by the investigators that the subject has completed treatment through the Week 12 visit window).

The primary efficacy analysis, to demonstrate the superiority of JNJ-64565111 compared to placebo on percentage reduction in body weight from baseline to Week 12, as well as all secondary efficacy analyses, will be based on the mITT analysis set.

A secondary analysis of the primary and secondary efficacy endpoints will be based on the ITT population (including data after initiation of rescue medication and data after the on-treatment period). This analysis will include all measurements through the Week 12 visit window. Supportive analyses based on the completers' analysis set will also be performed for the primary endpoint.

### **2.2.3. Safety Analysis Set**

The safety analysis set will include all randomized subjects who have received at least one dose of study drug.

### **2.2.4. Pharmacokinetics Analysis Set**

The PK analysis set includes treated subjects (received at least one dose of JNJ-64565111) who have at least one post baseline PK sample for analysis.

Pharmacokinetics analyses will be performed using the PK analysis set. Analysis will be based on actual treatment received.

### **2.2.5. Immunogenicity Analysis Set**

The immunogenicity evaluable (IE) analysis set includes treated subjects (received at least one dose of JNJ-64565111) who have a sample at baseline and at least 1 post-baseline sample for analysis. Immunogenicity analyses will use this analysis set. Analysis will be based on the actual treatment received.

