8.10. Further Assessments

8.10.1. Immunogenicity Assessments

The detection and characterization of anti-JNJ-64565111 antibodies will be performed using a validated assay method by or under the supervision of the sponsor. All samples collected for detection of anti-JNJ-64565111 antibodies will also be evaluated for JNJ-64565111 serum concentration to enable interpretation of the antibody data.

Anti-JNJ-64565111 antibodies will be evaluated in serum samples collected from all subjects according to the Schedule of Activities. Additionally, serum samples should also be collected at the final visit from subjects who are discontinued from treatment.

Serum samples will be screened for antibodies binding to JNJ-64565111 and the titer of confirmed positive samples will be reported. Other analyses may be performed to verify the stability of antibodies to JNJ-64565111 and/or further characterize the immunogenicity of JNJ-64565111.

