9.4.3. Other Analyses

Pharmacokinetic Analyses

If feasible, population PK analysis of serum concentration-time and exposure-response data of JNJ-64565111 may be performed using nonlinear mixed-effects modeling. Data may be combined with those of other selected studies to support a relevant structural model. Available baseline subject characteristics (demographics, laboratory variables, genotypes, race, etc.) will be tested as potential covariates affecting PK parameters. Details will be given in a population PK analysis plan, and the results of the population PK analysis will be presented in a separate report.

A snapshot date for PK samples to be analyzed will be defined, if required. Samples collected before this date will be analyzed for JNJ-64565111 and included in the population PK analysis. Samples collected after the snapshot date will be analyzed at a later date and may be included in a population PK re-analysis when they become available after database lock.

Data will be listed for all subjects with available serum concentrations per treatment group. Subjects will be excluded from the PK analysis if their data do not allow for accurate assessment of the PK (eg, lack of compliance with administration of the study drug; missing information of dosing and sampling times; concentration data not sufficient for PK parameter calculation).

All concentrations below the lowest quantifiable concentration or missing data will be labeled as such in the concentration database. All subjects and samples excluded from the analysis will be clearly documented in the study report.

For each treatment group, descriptive statistics, including sample size (n), arithmetic mean, geometric mean, SD, percent coefficient of variation, percent geometric coefficient of variation, median, minimum, and maximum will be calculated for serum concentrations for JNJ-64565111 at each time point.

Immunogenicity Analyses

The incidence of anti-JNJ-64565111 antibodies will be summarized for all subjects who receive at least 1 dose of JNJ-64565111 and have appropriate samples for detection of antibodies to JNJ-64565111.

A listing of subjects who are positive for antibodies to JNJ-64565111 will be provided. The maximum titers of antibodies to JNJ-64565111 will be summarized for subjects who are positive for antibodies to JNJ-64565111.

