### 1.1. Trial Objectives

#### Primary Objectives

The primary objectives are to assess the effects of JNJ-64565111 compared with placebo in severely obese subjects with Type 2 Diabetes Mellitus (T2DM) after 12 weeks of treatment on:

- the percentage change from baseline in body weight
- safety and tolerability

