## 7.2. Immunogenicity

Blood samples will be collected to examine the formation of antibodies to JNJ-64565111 at the specified visits (Day 1, Weeks 2, 6, 12, and 16) as shown in the schedule of events of the protocol. For subjects who discontinue SC study agent administrations, samples will be collected at their 4-week safety follow-up visit.

The data analysis of antibodies to JNJ-64565111 will be summarized if sufficient numbers of subjects are positive for antibodies and will include the following:

- The antibody status (positive, negative) of subjects will be summarized by JNJ-64565111 treatment groups. For subjects who discontinue SC study agent administrations and complete 4-week safety follow-up, a listing of their antibody status will be presented.
- The relationship between antibody to JNJ-64565111 status and efficacy and safety may be assessed at Week 12.
- $\geq 5\%$  and  $\geq 10\%$  weight loss response rates and % weight loss at Week 12 by antibody to JNJ-64565111 status and treatment group
- Injection site reaction by antibody to JNJ-64565111 status and treatment group.
- The relationship between antibody to JNJ-64565111 status at Week 6 and antibody to JNJ-64565111 status at Week 12 will be explored.
- The onset and duration of antibody to JNJ-64565111
- Figure of median serum JNJ-64565111 concentrations by antibody to JNJ-64565111 status.

Other analyses may be performed to verify the stability of antibodies to JNJ-64565111 and/or further characterize the immunogenicity of JNJ-64565111.

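### Antibodies are assayed in every arm but summarised only in drug-treated subjects, so the reported incidence has no concurrent placebo background rate

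*SAP*

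**What the plan says.** **Sampling and assay.** Protocol 8.10.1 states: "Anti-JNJ-64565111 antibodies will be evaluated in serum samples collected from all subjects according to the Schedule of Activities". Samples are screened in a validated assay, positives are confirmed, and titres are reported for the confirmed ones. SAP 7.2 gives the sampling times as Day 1 and Weeks 2, 6, 12 and 16.

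**Who is analysed.** SAP 2.2.5 says "The immunogenicity evaluable (IE) analysis set includes treated subjects (received at least one dose of JNJ-64565111") and adds a sample condition: subjects "who have a sample at baseline and at least 1 post-baseline sample for analysis". The scope is complete: "Immunogenicity analyses will use this analysis set". Protocol 9.4.3 has the same exposure condition: "The incidence of anti-JNJ-64565111 antibodies will be summarized for all subjects who receive at least 1 dose of JNJ-64565111", provided suitable samples exist.

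**What is displayed.** SAP 7.2: "The antibody status (positive, negative) of subjects will be summarized by JNJ-64565111 treatment groups". It also plans onset and duration of antibody, and weight loss and injection site reactions by antibody status. No placebo antibody summary appears in either document. Neither document defines a treatment-emergent antibody or says how a subject already positive on Day 1 is classified.

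**The concern.** An antibody incidence in drug-treated subjects mixes three things: reactivity present before dosing, positives produced by the assay during the study, and antibody raised by the drug. The baseline sample can separate the first. It cannot separate the second from the third when the result first turns positive at Week 2 or later. Placebo subjects bled on the same schedule and tested in the same assay are the direct estimate of that on-study background. The plan collects those results but does not report them.

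What is at stake is how a low or moderate incidence is read. A rate of a few per cent on drug means one thing if placebo shows none and another if placebo shows much the same.

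**Working it through.** **The plan's own figure.** The documents give no number for immunogenicity. The only relevant figure is the arm size in Protocol 9.2 and SAP 1.4: difference 2.7%, SD 4%, two-sided 0.05, 90% power.

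- n = 2 × (1.960 + 1.282)² × 4² / 2.7² = 46.1, rounded up to 47 per group.
- Power at 47 is 0.905 by the normal formula and 0.899 by the noncentral t with 92 degrees of freedom.

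This reproduces the plan. It fixes the largest possible denominators at 3 × 47 = 141 on drug and 47 on placebo, and says nothing more about the point.

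**Background positives.** The false-positive rate f per sample, after confirmation, is an assumption. There are four post-baseline samples. The chance that a subject with no drug-induced antibody is positive at least once is 1 − (1 − f)⁴ if samples are independent, and f if results are fully correlated within subject.

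| Assumed f | Correlation | Per subject | Expected of 141 on drug | Expected of 47 on placebo |
|---|---|---|---|---|
| 0.1% | full | 0.1% | 0.1 | 0.05 |
| 0.1% | none | 0.4% | 0.6 | 0.2 |
| 1% | full | 1.0% | 1.4 | 0.5 |
| 1% | none | 3.9% | 5.6 | 1.9 |
| 2% | full | 2.0% | 2.8 | 0.9 |
| 2% | none | 7.8% | 10.9 | 3.6 |

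If the correlation extended to the Day 1 sample as well, those subjects would already be positive at baseline and could be identified without placebo. The placebo column matters most for positives that come and go.

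**Share of positives unrelated to drug.** This needs a second assumption, the true drug-induced rate. At 5%, and adding the two rates:

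- Full correlation: 1/(1 + 5) = 17% to 2/(2 + 5) = 29%.
- Independence: 3.9/(3.9 + 5) = 44% to 7.8/(7.8 + 5) = 61%.

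At a true rate of 30%, even independence gives only 3.9/33.9 = 12% to 7.8/37.8 = 21%.

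**What a placebo column could show.** Exact two-sided 95% intervals with 47 subjects:

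- 0/47: upper limit 1 − 0.025^(1/47) = 7.5%.
- 1/47: 0.05% to 11.3%.
- 2/47: 0.5% to 14.5%.

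It could reveal a substantial background rate but could not exclude one of a few per cent.

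**The case against.** The exposed-only denominator is a deliberate and consistent choice. Protocol 9.4.3, SAP 2.2.5 and SAP 7.2 agree, and assaying everyone does not commit the plan to a placebo summary. That stands: this is an omission with a cheap remedy, not a contradiction between the documents.

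A reader might infer that the plan counts assay false positives and pre-existing reactivity as drug-induced. The documents do not support that. Nothing labels positives drug-induced or treatment-emergent. The set requires a baseline sample, positives are confirmed, and drug concentration is measured on the antibody samples to help interpret them. The SAP is silent on how baseline-positive subjects are classified. Taken alone, that silence is missing detail that analysts would probably fill sensibly.

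A reader might also infer that half or more of the positives would be unrelated to drug. That is one corner of the assumed range above. Full correlation, a lower error rate or a higher true rate each bring the share well down.

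The primary objective might seem to require a placebo comparison of antibodies, since "The primary objectives are to assess the effects of JNJ-64565111 compared with placebo" and safety is part of it. But neither document lists antibodies among the safety evaluations or analyses. Immunogenicity has its own sections.

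Finally, a placebo column would not remove false positives from the drug-arm tables of weight loss or injection site reactions by antibody status. SAP 7.2 also makes the antibody summaries conditional on enough positive subjects. Both points are correct. The column serves the reading of the incidence, not those tables.

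**Conclusion.** The point holds as a small, free improvement. The antibody incidence will lack a concurrent placebo background rate although placebo samples are drawn and evaluated, and the baseline sample does not fully replace that rate. Any statement of size rests on an assumed error rate. At 1–2% per sample over four samples, 1–2% to 3.9–7.8% of subjects would be positive at least once without drug effect, depending on within-subject correlation; at 0.1% the figure is at most 0.4%. The comparator has at most 47 subjects and is imprecise. The analysis is descriptive, with no bearing on the primary result, alpha or sample size.

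**What to change.** Amend SAP 2.2.5 and 7.2 as follows.

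1. Add treated placebo subjects who have a baseline and at least one post-baseline sample as a further comparator column in the antibody-status table. Leave the drug-group denominators as they are, so that Protocol 9.4.3 is still met.
2. In the same table, show by arm the number positive at baseline and the number treatment-emergent, meaning negative at baseline and positive later, or positive at baseline with a titre rise of a prespecified size.
3. Give the placebo rate with its exact 95% interval, so that its imprecision is visible.

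The cost is SAP wording, one column and a few rows. No samples or assays are needed beyond those in Protocol 8.10.1, where titres of confirmed positives are already reported.

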### 2.3. Definition of Subgroups

Subgroup analyses may be performed as defined below when there are at least 40 subjects within each subgroup category.

Subgroup	Definition
Sex	
 
female
 
male
 

Age	
 
18-59 years
 
60-70 years
 

Race	
 
White
 
Black or African American
 
Asian
 
Other
 

Baseline BMI	
 
<40 kg/m^2
 
≥40 kg/m^2
 

Baseline HbA 1c	
 
<8%
 
8% to <9%
 
9% to <10%
 
≥10%
 

Baseline fasting HOMA-IR	
 
≤ the median
 
> the median
 

### 2.4. Study Day and Relative Day

“Study Day 1” or “Day 1” refers to the day of the first study agent administration on or after the randomization date. All efficacy and safety assessments at all visits will be assigned a day relative to this date.

Study day or relative day for a visit is defined as:

- Visit date - (date of Study Day 1) +1, if visit date is ≥ date of Day 1
- Visit date - Date of Day 1, if visit date < date of Day 1

There is no 'Day 0'.

### 2.5. Baseline

Baseline is defined as the last observation prior to first administration of the study agent on or after the randomization date.

## 3. INTERIM ANALYSIS AND DATA MONITORING COMMITTEE REVIEW

A pre-planned interim analysis was performed in Study 64565111OBE2001; at the time of the interim analysis, available unblinded safety data from this study (64565111OBE2002) was reviewed by the DMC. These analyses were described in a separate DMC SAP.

## 4. SUBJECT INFORMATION

The number of subjects in each analysis set will be summarized and listed by treatment group, combined JNJ-64565111 treatment group and overall. In addition, a frequency table of the number of subjects by site will be presented.

### 4.1. Demographics and Baseline Characteristics

Table 4.1.1 presents a list of the demographic variables that will be summarized by treatment group, combined JNJ-64565111 treatment group, and overall for the ITT analysis set, mITT analysis set, safety analysis set, completers' analysis set, and PK analysis set.

**Table 4.1.1: Demographic Variables**

Continuous Variables	Summary Type
Age (years)	Descriptive statistics (N, mean, standard deviation [SD], median and range [minimum and maximum]).
Weight (kg)	
Height (cm)	
Body Mass Index (BMI) (kg/m  )	
Waist circumference (cm)	
Pulse rate (bpm)	
Systolic Blood Pressure (mmHg)	
Diastolic Blood Pressure (mmHg)	
Rate pressure product (bpm*mmHg)	
eGFR (mL/min/1.73m  )	
HbA 1c (%)	
FPG (mmol/L)	
Fasting insulin (pmol/L)	
Duration of diabetes (years)	
Duration of oral antidiabetic treatment prior to study entry (years)	
HOMA-B	
HOMA-IR	
Fasting C-peptide (nmol/L)	
Fasting serum lipids: total cholesterol, triglycerides, high-density-lipoprotein cholesterol (HDL-C), low-density-lipoprotein cholesterol (LDL-C)	
IWQOL-Lite physical function domain score	
Beta-hydroxybutyrate (mmol/L)	
Categorical Variables	Summary Type
Age (18-30 years, 31-50 years, 51-64 years, and ≥65 years)	Frequency distribution with the number and percentage of subjects in each category.
Age for analysis (18-59 years and ≥60 years)	
Sex (male, female)	
Race a (White, Black or African American, Asian, American Indian or Alaska Native, Native Hawaiian or other Pacific Islander, Multiple, Other)	
Race for analysis (White, Black or African American, Asian, and Other)	
Ethnicity (Hispanic or Latino, Not Hispanic or Latino, Unknown, Not reported)	
Baseline BMI (<40, ≥40 kg/m  )	
Baseline HbA 1c (<8%, 8% to <9%, 9% to <10%, ≥10%)	
Baseline fasting HOMA-B (≤ the median, > the median)	
Baseline fasting HOMA-IR (≤ the median, > the median)	
Baseline eGFR (<90, ≥90 mL/min/1.73m  )	
Baseline SBP (<140 mmHg, ≥140 mmHg)	

a If multiple race categories are indicated, the Race is recorded as 'Multiple'

## 4.2. Disposition Information

The number of subjects in the following disposition categories will be summarized by treatment group and overall:

- Subjects randomized;
- Subjects in the ITT analysis set;
- Subjects in the mITT analysis set;
- Subjects in the completers' analysis set;
- Subjects in the mITT analysis set who discontinue from treatment before the Week 12 visit (i.e. investigator indicates on the eCRF [treatment disposition page] that the subject discontinued from the treatment);
- Subjects in the mITT analysis set who discontinue from study before the Week 12 visit (i.e., investigator indicates on the eCRF [trial disposition page] that the subject discontinued from study);
- Subjects in the mITT analysis set who receive glycemic rescue therapy (documented in the eCRF by investigator) before the Week 12 visit;
- Subjects in the safety analysis set

For subjects who discontinue from the study after randomization, the corresponding reasons for (1) discontinuation from the treatment and (2) discontinuation from the study during the 12-week treatment phase will be summarized.

The distribution of the time to study discontinuation for the 12-week treatment phase will be displayed with Kaplan-Meier curves. Subjects who terminate study participation prematurely at any time will be considered an 'event' and their date of study discontinuation will be used in the time to event calculation. Subjects who complete the study will be censored on their date of study completion. Descriptive analyses for the time to early discontinuation will be provided.

Listings of subjects will be provided for the following categories:

- Subjects who discontinued from treatment
- Subjects who discontinued from the study prematurely
- Subjects who were unblinded during the study period
- Subjects who were randomized but did not receive treatment.

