- Initiation and planned continued use of disallowed therapy (see Section [6.5](#), Prestudy and Concomitant Therapy)
- Subject is on glycemic rescue therapy, and after at least 2 weeks on the maximum dose considered appropriate by the investigator, FPG is >180 mg/dL (10.0 mmol/L)

- Subject experiences a SAE of biochemically-confirmed (eg, blood pH, serum β -hydroxybutyrate, anion gap) DKA
- Subject experiences an episode of vomiting assessed as “severe” lasting more than 24 hours and considered to be at least possibly related to study drug without any other potential cause (eg, viral gastroenteritis, food-borne illness).

Subjects who prematurely discontinue study drug prior to Week 12 will require an immediate EOT assessment (either on the day of study drug discontinuation or as soon as possible following study drug discontinuation) and the SAE assessment/follow-up and PK and immunogenicity (ie, ADA) collection at least 5 weeks since the last dose of study drug.

Subjects that discontinue study drug early will continue in the study (off treatment) and will be assessed at the subsequent visit(s) as described in the Schedule of Activities schedule, starting at the next scheduled visit from when study drug was permanently discontinued up to the final Week 12 visit. These off-treatment visits will include assessment and collection of:

- SAEs
- Specific AEs of interest (ie, MACE events, acute pancreatitis, and possible cases of thyroid neoplasm)
- Vital signs (including body weight)
- Concomitant medications

If subjects that discontinued study drug early are unable to return to their site for the scheduled on-site study visit, an alternate contact visit should be conducted with the goal of collecting any SAEs, MACEs (ie, CV death, nonfatal MI and nonfatal stroke), acute pancreatitis, and AEs of thyroid neoplasm. Details regarding discussions via telephone, email, or other methods of contact should be properly documented on subject’s source record and/or eCRF, including date of contact, outcome and responses provided by the subjects. The site may consult subjects’ delegated contact(s) for the off-treatment follow-up if the site is unable to reach the subjects after multiple attempts.

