7.2. Discontinuation from the Study

A subject will be discontinued from the study for any of the following reasons:

- Lost to follow-up
- Withdrawal of consent
- Death

When a subject is discontinued from the study, the reason for early study discontinuation is to be documented in the eCRF and in the source document. Study drug assigned to a subject who discontinued from the study may not be assigned to another subject. Subjects who discontinued from the study will not be replaced.

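### SAP 4.2 disposition displays under-represent treatment discontinuation: the counts sit on the mITT set, and the reasons and Kaplan-Meier displays follow leaving the study, not stopping drug

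*SAP*

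**What the plan says.** SAP 4.2 sets out three summary displays and a set of listings.

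- **Counts by group.** One line is "Subjects in the mITT analysis set who discontinue from treatment before the Week 12 visit", taken from the treatment disposition eCRF page. The lines for study discontinuation and for glycemic rescue are also limited to mITT. The randomized, ITT, mITT, completers' and safety sets are counted, but discontinuation is not broken down within the randomized or safety set.
- **Reasons.** "For subjects who discontinue from the study after randomization, the corresponding reasons for (1) discontinuation from the treatment and (2) discontinuation from the study" are to be summarized for the 12-week phase.
- **Timing.** "The distribution of the time to study discontinuation for the 12-week treatment phase will be displayed with Kaplan-Meier curves". Leaving the study early is the event, dated at study exit. Subjects who complete the study are censored.
- **Listings.** These include "Subjects who discontinued from treatment", without an mITT or study-exit restriction.

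SAP 2.2.2 defines mITT as "all ITT subjects who have taken at least one dose of study medication and have at least 1 post-baseline body weight measurement". The safety set (SAP 2.2.3) needs one dose and no weight.

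Protocol 7.1 keeps a subject who stops drug in the study, off treatment, with visits up to Week 12. Protocol 7.2 states "A subject will be discontinued from the study for any of the following reasons" and names three: loss to follow-up, withdrawal of consent and death. Protocol 4.4 treats anyone assessed through Week 12 as having completed the study.

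**The concern.** Stopping drug and leaving the study are different events in this trial by design. A subject who stops for any reason other than death, and neither withdraws consent nor is lost, remains a study participant. Displays built on study exit therefore describe retention, and a display built on mITT depends on what happened after dosing.

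Safety and tolerability is a primary objective, and the trial is meant to inform Phase 3 dose selection (Protocol 2.1). Doses are fixed without titration (Protocol 6.7), and Protocol 4.3 cites a dose-dependent increase in gastrointestinal events among its grounds for limiting the top dose. How many subjects stop drug in each arm, when, and for what reason is a result that readers will look for in the disposition section. As written, that section gives the count on a selected denominator, the reasons for only some of those who stop, and the timing of a different event.

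**Working it through.** **Inputs.** The arm size is 47 (SAP 1.4). That is the only design figure involved, and it reproduces: n = 2 × (1.960 + 1.282)² × 4² / 2.7² = 46.1, rounded up to 47. Power at 47 per group is 90.5% by the normal approximation and 89.9% by the noncentral t. The documents state no discontinuation rate, no share without a post-baseline weight and no share leaving the study, so these are assumed and shown over a range.

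**1. The mITT denominator.** Let D of n treated subjects stop drug, and let x of those D have no post-baseline weight. The plan reports (D − x)/(n − x) in place of D/n. For D < n and x > 0 this is always lower, because the removed subjects are all stoppers.

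| D of 47 | On all treated | x = 1 | x = 2 | x = 3 |
|---|---|---|---|---|
| 5 | 10.6% | 4/46 = 8.7% | 3/45 = 6.7% | 2/44 = 4.5% |
| 10 | 21.3% | 9/46 = 19.6% | 8/45 = 17.8% | 7/44 = 15.9% |
| 15 | 31.9% | 14/46 = 30.4% | 13/45 = 28.9% | 12/44 = 27.3% |

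With x = 0 there is no loss. With D = 10 the loss is 0 to 5.4 percentage points.

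How large x could be is limited by the protocol. Stopping drug calls for an immediate end-of-treatment visit, weight is scheduled at that visit, and off-treatment visits also include weight. The SAP's mITT accepts a weight taken off drug. On the other side, the first routine post-baseline weight is at Week 2, and a stopper who cannot attend may be followed by telephone or email for safety events only (Protocol 7.1). So x is probably small but need not be zero.

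**2. Reasons and Kaplan-Meier.** Let s be the share of the D stoppers who also leave the study. The reasons summary holds s × D of them, and the curve counts the same s × D as events. With D = 10:

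| s | Captured | Share of the arm |
|---|---|---|
| 20% | 2 of 10 | 4.3% |
| 50% | 5 of 10 | 10.6% |
| 80% | 8 of 10 | 17.0% |
| 100% | 10 of 10 | 21.3% |

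This can be the larger effect, because the protocol intends stoppers to stay. Even for those captured, the curve uses the date of leaving the study, which may fall after the last dose.

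**3. The displays select different people.** The count line loses stoppers who are never weighed again; the reasons summary loses stoppers who stay. Suppose 3 of 10 stoppers are never weighed and leave the study, and the other 7 remain to Week 12. The count line then shows 7 and the reasons summary describes the other 3, with no subject in common.

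**4. What other sections supply.**

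- *Adverse events (SAP 6 and 6.1, safety set).* Tables of AEs leading to discontinuation, drug-related AEs leading to discontinuation and AEs by action taken cover AE-related stopping in full. They need not cover the other stopping reasons in Protocol 7.1, such as persistent poor compliance, formal unblinding, disallowed therapy or inadequate glycemic control on rescue.
- *Exposure (SAP 4.4, safety set).* Duration is last dose − first dose + 8 days. Stopping after the tenth weekly dose (Day 64) gives 63 + 8 = 71 days; a twelfth dose on Day 78 gives 77 + 8 = 85 days. Both fall in the top category of at least 10 weeks. Earlier stopping is visible there, but without reasons.
- *Listing of treatment stoppers.* This is complete, but gives no rate by dose.

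**The case against.** The strongest reply is that SAP 4.2 is not the tolerability analysis. A subject who stops for vomiting and attends Week 12 is counted in the SAP 6.1 tables whatever the mITT or study status. Nausea, vomiting and diarrhea also have combined-term analyses. A reader might infer from SAP 4.2 that intolerance is under-counted in the trial as a whole. The documents do not support that: AE-related stopping is tabulated on all treated subjects, exposure is on the same set, and all treatment stoppers are listed. This part of the reply stands in full.

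Second, the all-cause count can nearly be recovered. The same table gives the safety set and the completers' set, which is defined by completed treatment on the eCRF, so the difference approximates the number stopping drug (47 − 37 = 10 in the illustration). This stands as a workaround. A reader should not have to derive the figure by subtraction, and the subtraction yields neither reasons nor timing.

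Third, a subject never weighed again has often been lost or has withdrawn. Such a subject would appear in the reasons summary and the curve, neither of which is stated to be limited to mITT. This also stands: the gaps partly offset across displays. It does not make any one display complete.

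Fourth, a reader might infer that the Kaplan-Meier curve is wrong. It is not. It is a legitimate retention display, and censoring an off-drug Week 12 attender is right for its event. What is missing is a companion curve.

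Nor do the documents show that the loss would be greater at particular doses. That is possible, but nothing in them quantifies it.

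**Conclusion.** The point holds for the SAP 4.2 displays and no further. Followed as written, they give a discontinuation count on a denominator selected after randomization, a reasons summary that omits subjects who stop drug and stay, and no time-to-event display of stopping drug. The affected results are the all-cause rate, the non-AE reasons and the timing of treatment discontinuation by dose. The AE tables on the safety set are untouched.

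If 10 of 47 stopped drug, the reported rate would lie between 15.9% and 21.3%, for 3 down to 0 lacking a weight. The reasons summary and the curve would represent 2 to 10 of the 10, for 20% to 100% also leaving the study. All these counts are assumptions. The required end-of-treatment weight makes the first effect likely small. The second depends on how well the protocol's aim of keeping stoppers in the study succeeds: the better the retention, the less these displays show.

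**What to change.** Amend SAP 4.2 in three places.

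1. Base the treatment-discontinuation, study-discontinuation and rescue counts on the safety set, or on the all-randomized set, by treatment group. The mITT lines can stay as a supplement.
2. Tabulate reasons for treatment discontinuation for every subject who discontinues treatment, and tabulate reasons for study discontinuation separately.
3. Add a Kaplan-Meier curve of time to treatment discontinuation by group, and keep the existing study-discontinuation curve beside it.

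The cost is SAP wording and one additional display. The treatment disposition eCRF page and the dosing records already hold what is needed, so no new data are required.
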